9.4.3 Safety

Safety analyses will be performed using the safety analysis set. Safety data will be presented using descriptive statistics unless otherwise specified.

Verbatim terms of AEs will be coded to a standardised PT using the MedDRA version in force at DBL.

The overall number and percentage of subjects with AEs and SAEs will be presented. The occurrence of AEs and SAEs will be described also by SOC, PT and separately by severity and by relationship to the IP (as determined by the Investigator). Should a subject report the same PT/SOC within multiple severity or relationship categories, the subject's worst occurrence (most severe/most related) will be tabulated.

Serious AEs, AEs leading to death, AEs leading to withdrawal from study, commonly occurring AEs and AESIs will be summarised by SOC and PT.

Laboratory data, including serum chemistry, haematology and urinalysis will be summarised by presenting summary statistics of observed and change from baseline values at each scheduled assessment visit. Shift tables using normal ranges (baseline to most extreme postbaseline value) will also be presented. The incidence of clinically notable laboratory abnormalities will be summarised. Shift tables will also be provided.

Number of subjects with elevated liver function tests that meet the HL definition will be summarised and evaluated.

Vital signs data will be summarised by presenting summary statistics of observed and change from baseline values at each scheduled assessment visit. The incidence of clinically notable vital signs abnormalities will be summarised.

Abnormal ECGs as per Investigator's overall interpretation will be summarised using frequency and percentage of subjects.

Additional analyses assessing the impact of COVID-19 may be included in the SAP.

9.4.4 Other Analyses

There are no other analyses planned for this study.

9.5 Interim Analyses

There are no interim analyses planned for this study.

9.6 Data Monitoring Committee

The use of an Independent Data Monitoring Committee is not foreseen for this study.

AUC _{0-inf}	Area under serum concentration-time curve from time zero (predose) extrapolated to infinity
AUC _{0-last}	Area under the concentration-time curve from time zero (predose) to the last measurable concentration
AUMC _{0-inf}	Area under the moment curve of the analyte in the sampled matrix from zero (predose) extrapolated to infinite time
AZ	AstraZeneca
BLQ	Below the LLOQ
CL/F	Apparent clearance
C _{max}	Maximum observed serum concentration
CSP	Clinical study protocol
CSR	Clinical Study Report
CV%	Coefficient of variation
DBL	Database lock
ECG	Electrocardiogram
EOS	End of Study
CCI	[REDACTED]
	[REDACTED]
	[REDACTED]
GCV% or GeoCV%	Geometric coefficient of variation
IP	Investigational product
LLOQ	Lower limit of quantification
λ _z	Elimination rate constant
max	Maximum
MedDRA	Medical Dictionary for Regulatory Activities
min	Minimum

Abbreviation or special term	Explanation
MRD	Minimum required dilution
MRT	Mean residence time
nAb	Neutralising antibodies
ND	Not Determined
CCI	[REDACTED]
PD	Pharmacodynamic
PK	Pharmacokinetic(s)
CCI	[REDACTED]
PT	Preferred term
Rsq	Goodness of fit statistic for calculation of λ_z
SAE	Serious adverse event
SAP	Statistical analysis plan
SC	Subcutaneous
SD	Standard deviation
SI	Standard international
SOC	System organ class
$t_{1/2}$	Terminal phase elimination half-life
TBL	Total bilirubin
TE-ADA	Treatment-emergent anti-drug antibodies
t_{max}	Time to achieve maximum observed serum concentration
ULN	upper limit of the normal
V_{ss}/F	Apparent steady-state volume of distribution
V_z/F	Apparent volume of distribution

AMENDMENT HISTORY

Category*: Change refers to	Date	Description of change	In line with the CSP?	Rationale
Other	01-Aug-22	Section 6: Text has been updated to include Day 29 PK analysis for dose confirmation for safety and efficacy study in 5 to <12 years old children.	No	Day 29 PK analysis after all subjects complete Visit 7 was introduced in order to provide faster confirmation for dose of IP for future safety and efficacy study in 5 to <12 years old children.
Other	01-Aug-22	Section 5: Updated text to “No formal interim analyses are planned in this trial”.	Yes	Text added to clarify no formal interim analyses to be conducted.
Other	01-Aug-22	Study details: CSP version updated.	Yes	CSP version was updated to align with the latest one.
Other	01-Aug-22	Section 4.2.2: Removed OCS details and added details of ICS dose conversion factors.	Yes	OCS details removed to be consistent with Exclusion Criterium #6, reference of ICS conversion dose factors added to keep track of version used.
Other	01-Aug-22	Section 4.2.6.1: Removed text “A summary of the most common AEs will be presented by PT.”.	N/A	Due to little sample size, the marginal percentage of most common AEs as required per template would be unreasonably high.
Other	01-Aug-22	Section 4.2.6.2: Removed text “For urinalysis data, a shift table will be generated to present changes from baseline to maximum post-baseline value for each quantitative variable and will include subjects with	N/A	Urinalysis data is no longer collected in terms of quantitative variables for which this text was included. Respective shift table for negative/positive values remains included in the text of this SAP.

		both baseline and post-baseline data.”		
Data presentations	01-Aug-22	Section 4.2.6.2: Removed TBL presentations as multiples of ULN $\leq 1.5, >1.5-2, >2$ and AST/ALT as multiples of ULN $\leq 1, >1-3, >3-5, >5-10, >10$.	N/A	These ranges for ULN are not used in any outputs, actually used ranges remain a part of this SAP.
Data presentations	01-Aug-22	Sections 4.2.6.2 and 4.2.6.3: Missing values category and baseline to last post-baseline value shift table removed for clinical laboratory and vital signs.	N/A	Shift tables for baseline to minimum/maximum post-baseline value are sufficient for this study. Missing values category does not provide valuable information in shift table.
CCI				
Data presentations	01-Aug-22	Section 4.2.1.2: Removed virology results at screening (HBsAg, HCAb, HIV-1, and HIV-2 antibodies) from baseline characteristics summary.	N/A	This data is no longer presented due to privacy reasons.

* Pre-specified categories are
Primary or secondary endpoints; Statistical analysis method for the primary or secondary endpoints; Derivation of primary or secondary endpoints; Multiple Testing Procedure; Data presentations; Other

1 STUDY DETAILS

This is the statistical analysis plan (SAP) for study D5180C00025. The SAP describes the statistical analyses specified in version 4.0 of the clinical study protocol (CSP) in more detail; any changes with regards to what is already specified in the CSP will be described in [Section 6](#) of this document.

1.1 Study Objectives

1.1.1 Primary Objective

Primary objective:	Endpoints/variables:
To describe the pharmacokinetic (PK) parameters following a single subcutaneous (SC) administration of tezepelumab CCI in children with mild, moderate, or severe asthma	
Maximum concentration (C_{max})Time to C_{max} (t_{max})Area under the concentration-time curve (AUC)Terminal phase elimination half-life ($t_{1/2}$)Apparent clearance (CL/F)Apparent steady-state volume of distribution (V_{ss}/F)

1.1.2 Secondary Objective

Secondary objective:	Endpoints/variables:
To evaluate the immunogenicity of tezepelumab	
Presence of anti-drug antibodies (ADA)

1.1.3 Safety Objective

Safety objective:	Endpoints/variables:
To evaluate the safety and tolerability following a single SC administration of tezepelumab CCI	
Adverse events /serious adverse eventsVital signsLaboratory parametersElectrocardiogram (ECG)

1.1.4 Exploratory Objective

Exploratory objective:	Endpoints/variables:
CCI [REDACTED]	[REDACTED]
	[REDACTED]
	[REDACTED]
	[REDACTED]
	[REDACTED]

1.2 Study Design

This is a multicentre, open label study designed to evaluate the PK profile of tezepelumab following a single SC CCI [REDACTED] dose in children aged ≥ 5 to 11 years with mild, moderate, or severe asthma.

Approximately 24 subjects will be enrolled and approximately 14 paediatric subjects aged ≥ 5 to 11 years (inclusive) will receive a single SC CCI [REDACTED] dose of tezepelumab in an attempt to have at least 12 paediatric subjects complete the study. At least 4 subjects will have body weight < 25 kg and a minimum of 3 subjects will have body weight ≥ 25 kg to < 40 kg.

Subjects who are eligible to participate but do not go on to receive tezepelumab, or subjects who do not complete the required evaluations through to Day 85 may be replaced to maintain the stipulated number of evaluable subjects, at the discretion of the Sponsor.

[figure not shown]
The 99-day study consists of:

- A consent/screening period of up to 14 days
- Treatment and follow-up period of 85 days.

The study design is summarised in [Figure 1](#).

Subjects will attend the study site and informed consent will be obtained from the legal representative and informed assent will be obtained from the subject. Screening assessments should be completed within 14 days (Day -14 to Day -1). Subjects who meet eligibility criteria will receive a single SC CCI [REDACTED] dose of tezepelumab, administered in the anterior thigh by a healthcare professional on Day 1 and remain at the study centre for 2 hours after dosing. The subjects will then return to the centre for outpatient Follow-up visits on Days 3, 7, 11, 15, 29, 57, and 85 (End of Study [EOS]). The study will be completed after the EOS visit on Day 85.

Figure 1 Study Design

1.3 Number of Subjects

No formal sample size calculation was conducted for this study. The number of subjects was based on the desire to obtain adequate PK and safety data while exposing as few paediatric subjects as possible to tezepelumab and study procedures. A total of 12 subjects treated with tezepelumab is considered sufficient to provide adequate data to characterise PK of tezepelumab in children aged \geq 5 to 11 years. At least 4 subjects will have body weight $<$ 25 kg and a minimum of 3 subjects will have body weight \geq 25 kg and $<$ 40 kg. Approximately 14 subjects will receive tezepelumab in an attempt to have at least 12 subjects complete the study.

Subjects who are eligible to participate but do not go on to receive tezepelumab, or subjects who do not complete the required evaluation through to Day 85 may be replaced to maintain the stipulated number of evaluable subjects, at the discretion of the Sponsor. In addition, subjects may be replaced when factors such as important protocol deviations are deemed to affect evaluability of subject's PK profile. Examples include, but may not be limited to, incorrect IP dose administered resulting in all PK data from the subject being unevaluable, or PK sample(s) collection missed or collected not in accordance with the protocol.

All decisions to replace a subject will be documented in a Note to Study File.

2 ANALYSIS SETS

2.1 Definition of Analysis Sets

Analysis sets will be defined as follows.

2.1.1 Enrolled Analysis Set

This analysis set will consist of all subjects who sign the informed consent form (ICF) and will be used for reporting of overall disposition and listings including screen failures.

'Enrolled' means a subject's, and their legally acceptable representative's, agreement to participate in a clinical study following completion of the informed consent process. Potential

subjects who are screened for the purpose of determining eligibility for the study but are not assigned to treatment in the study, are considered ‘screen failures’.

2.1.2 Safety Analysis Set

The safety analysis set will consist of all subjects who receive at least one dose of tezepelumab.

Anti-drug antibodies, PD parameter summaries and safety presentations will be based on the safety analysis set.

2.1.3 Pharmacokinetic Analysis Set

The PK analysis set will include all subjects in the Safety Analysis set that have at least one detectable tezepelumab serum concentration from a sample collected post-dose that is assumed not to be affected by factors such as important protocol deviations (e.g., incorrect dose of study IP received).

Protocol deviations that occur during the study will be considered for their severity/impact on the analysis of PK data and will be taken into consideration when subjects are assigned to the PK analysis sets.

All PK summaries will be based on the PK analysis set.

2.2 Violations and Deviations

Important protocol deviations will be defined at subject level prior to database lock (DBL) and will be tabulated and listed. In addition, a listing of all COVID-19 related protocol deviations (important and non-important) will be provided. Screen failures will not be included in above listings.

Important protocol deviations are defined as PDs which may significantly affect the completeness, accuracy and/or reliability of the study data, or which may significantly affect a subject’s rights, safety or well-being. The definitions of each category of important protocol deviation will be fully specified in the Protocol Deviations Management Plan (PDMP) and will include (but may not be limited to):

- subjects enrolled without fulfilling key entry criteria;
- subjects who received prohibited or restricted concomitant medications during the study;
- subjects who received the incorrect IP dose.

Important Protocol Deviations will not be a condition to exclude any subject from the safety analysis set, nor to exclude any data from subjects included in the safety analysis set.

The exclusion of any subjects from the PK analysis set, or the exclusion of selected time-points only from subjects in the PK analysis set from the calculation of the PK parameters and/or from the PK summary statistics will be documented by the PK Scientist including the reason(s) for exclusion. All exclusions will be reported in the data listings.

The available concentration data and PK parameter data for any subjects excluded from the PK analysis set will be listed only. Data excluded from subjects who are included in the PK analysis set will be excluded from summary statistics and will be listed only. However, in the event that no PK parameters can be calculated for a subject from the available data, there will not be any parameters included in a listing.

In the event that a PK sample is missing for a subject, the IQVIA Pharmacokineticist and sponsor will evaluate the PK samples collected (collection times only, not concentrations) for the subject and determine if enough samples were collected to report some or all of the protocol defined PK parameters.

The following people, at a minimum, must review the sample collection times for subjects that miss one or more PK samples to determine if a replacement subject is needed:

- Sponsor Clinical Pharmacologist or PK Specialist,
- IQVIA Pharmacokineticist.

3 PRIMARY AND SECONDARY VARIABLES

3.1 General Principles

3.1.1 Baseline Definitions

Baseline is defined as the last valid non-missing result obtained on or prior to the date of dosing of tezepelumab.

If there is no result prior to dosing of tezepelumab, then the baseline value will not be imputed and will be set to missing.

Absolute change from baseline is defined as the difference between the relevant post-baseline value and the baseline value. If either the post-baseline value or the baseline value is missing, then the absolute change from baseline will also be missing.

Unless specified otherwise, "change from baseline" is assumed to be the absolute change from baseline.

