** Visit 1 and Visit 2 local COVID-19 viral rapid test results must be negative prior to spirometry, **CCI** [REDACTED], and IP administration at V2.

a Complete physical examination to be performed.

b Brief physical examination to be performed.

c Vital signs (blood pressure, heart rate, respiratory rate and body temperature) will be assessed within 1 hour prior to and at 1 hour and 2 hours post-IP administration.

d **CCI** [REDACTED] (Section 8.5.3).

e Pregnancy tests (serum and urine) to be performed for females of childbearing potential.

f Serum sample for PK analysis will be collected within ± 1 hour of the time the baseline Day 1 sample was collected, on Days 3, 7, 11, 15, 29, 57 and 85/EOS.

g Serum sample for PK analysis to be taken within 1 hour prior to IP administration on Day 1.

h Serum sample for determination of ADA; if positive for ADA, may be analysed for nAb (Section 8.5.2). In the event of suspected immunologically-related AE, an unscheduled ADA sample will be collected.

i Serum sample for immunogenicity analysis will be collected within ± 1 hour of the time the baseline Day 1 sample was collected, on Day 29 and Day 85/EOS.

j Serum sample for immunogenicity analysis to be taken within 1 hour prior to IP administration on Day 1.

k Local COVID-19 viral rapid test must be available and negative prior to IP administration at V2.

l Urinalysis will be performed at site via dipstick. If any parameter is abnormal, the urine sample will be sent to the central laboratory for further microscopy and culture analysis.

m The local COVID-19 viral rapid test should be able to provide results in less than 60 minutes. Refer to Section 8.2.5.2 for additional details

n Subjects/caregivers must be contacted by telephone for COVID-19 screening assessment within 24 hours prior to every study visit, regardless of on-site or remote

o **CCI** [REDACTED]

ADA Anti-drug antibodies; AE Adverse event; BD Bronchodilator; β-HCG Beta-human chorionic gonadotrophin; COVID-19 Coronavirus Disease 2019; CSP Clinical Study Protocol; ECG Electrocardiogram; EOS End of Study; **CCI** [REDACTED]; HBsAg Hepatitis B surface antigen; HCAb Hepatitis C antibody; HIV-1/-2 Human immunodeficiency virus; IgE Immunoglobulin E; IP Investigational product; nAb Neutralising antibodies; **CCI** [REDACTED]; PD Pharmacodynamic; PK Pharmacokinetic; **CCI** [REDACTED]; SAE Serious adverse event; SID Subject identification; V Visit.

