2.3.1 Risk Assessment

Clinical and nonclinical experience with tezepelumab demonstrates no safety or tolerability concerns to date. Potential risks based on the mechanism of action of tezepelumab include serious infections, helminth infections, and serious hypersensitivity reactions. Risk minimisation strategies associated with tezepelumab have been identified, described in the current IB and are included in this protocol. The risk mitigation strategies include but are not limited to: monitoring the subject for vital signs for a minimum of 2 hours post-IP, following each subject at every visit for AEs, as well as frequent study visits in the days following the administration of IP allowing for more intense monitoring of the subject by eg, physical examinations, ECGs, urinalysis, serum chemistry and haematology. Additional risks associated with the conduct of the study (eg, collection of blood for safety, PK and PD assessments, and spirometry testing) have a minimal impact on subjects in the study.

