8.2.2 Vital Signs

Vital signs will be performed at timelines as specified in the SoA ([Table 1](#)). If required, this may be done by a study nurse at the subject's home on the Day 11 visit, if previously approved and agreed with AstraZeneca.

Vital signs (blood pressure [BP], heart rate, respiratory rate and body temperature) will be obtained in accordance with SoA.

On Day 1, vital signs will be assessed within 1 hour prior to and at 1 hour and 2 hours post-IP administration.

Vital signs will be taken prior to blood drawing, and, if possible, usual asthma controller medication.

Blood pressure and pulse measurements will be assessed in sitting position with a completely automated device. Manual techniques will be used only if an automated device is not available.

Blood pressure and pulse measurements should be preceded by at least 5 minutes of rest for the subject in a quiet setting without distractions (eg, television, cell phones).

Pulse rate will be obtained before BP, if the manual measurement technique is used.

Respiration rate will be obtained after the subject has been resting for at least 5 minutes, by counting number of breaths (ie, how many times the chest rises) for one minute.

Body temperature will be measured prior to IP administration, in accordance with local standards.

See Section [8.3.5](#) for reporting AEs based on vital signs.

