Important protocol deviations will be defined at subject level prior to DBL and will be summarised and listed. The definitions of each category of important protocol deviation will be fully specified in the study Non-Compliance Handling Plan and will include (but may not be limited to): subjects who received IP without fulfilling key entry criteria; subjects who received prohibited or restricted concomitant medications during the study; subjects who received the incorrect IP dose.

In general, the last valid non-missing measurement taken on or prior to the date of treatment will serve as the baseline measurement. If there is no value on or prior to the date of treatment, then the baseline value will not be imputed and will be set to missing.

Absolute change from baseline is defined as the difference between the relevant post-baseline value and the baseline value. Unless specified otherwise, “change from baseline” is assumed to be absolute change from baseline.

Further details regarding baseline and/or change from baseline definitions will be provided in the SAP.

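### SAP 3.1.1 ties baseline to the date of dosing, so as worded the vital-signs baseline is a post-dose reading, which conflicts with the section's own next sentence

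*SAP*

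**What the plan says.** **Baseline.** SAP 3.1.1 opens with "Baseline is defined as the last valid non-missing result obtained on or prior to the date of dosing of tezepelumab". It continues: "If there is no result prior to dosing of tezepelumab, then the baseline value will not be imputed and will be set to missing". The first sentence tests the calendar date; the second refers to dosing itself.

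Protocol 9.4.1 has the same date-level test, offered as a general rule: "the last valid non-missing measurement taken on or prior to the date of treatment will serve as the baseline measurement". It leaves the detail to the SAP: "Further details regarding baseline and/or change from baseline definitions will be provided in the SAP".

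**Vital signs on the dosing date.** Protocol 8.2.2: "On Day 1, vital signs will be assessed within 1 hour prior to and at 1 hour and 2 hours post-IP administration". Footnote c to the Schedule of Activities gives the same times and includes temperature: "Vital signs (blood pressure, heart rate, respiratory rate and body temperature) will be assessed within 1 hour prior to and at 1 hour", and then at 2 hours. Protocol 8.2.2 also lists temperature among the vital signs, but has a separate line placing the temperature measurement before IP.

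**Use of baseline.** SAP 3.4.3 calculates changes from baseline to each later scheduled assessment. SAP 4.2.6.3 adds shift tables from baseline to the post-baseline maximum and minimum for diastolic and systolic pressure, pulse, respiratory rate and temperature. Neither section sets its own vital-signs baseline or names the Day 1 post-dose time points.

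**Related rules.** The on-study period in SAP 3.1.3 starts on the date of IP administration. SAP 3.1.4 prefers the earliest of several timed values on one day, but for choosing a visit's value within an analysis window, and its Table 1 gives windows only for V4 to V9.

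**The concern.** A date-level baseline is harmless when an assessment is done once on the dosing day, before dosing. It fails when the assessment is repeated after dosing that day, because the last result on that date is then a treated one. In the readable schedule, vital signs are the only assessment with a scheduled post-dose repeat on Day 1.

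Vital signs are a listed safety endpoint, and Protocol 2.3.1 names "monitoring the subject for vital signs for a minimum of 2 hours post-IP" as a risk mitigation. The 1-hour and 2-hour readings are the scheduled readings in that period. A table that uses one of them as the reference cannot show it as a change from the untreated state, and every later change is taken from that treated value.

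**Working it through.** The plan gives no figure to reproduce. The check applies the wording to the schedule.

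**Step 1. Which reading is baseline?** Inputs: SAP 3.1.1, Protocol 8.2.2 and Schedule footnote c. Compare the first sentence (last result dated on or before the dosing date) with a clock-time rule (last result before the dose).

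| Readings available | First sentence as worded | Clock-time rule |
|---|---|---|
| Screening, Day 1 pre-dose, +1 h, +2 h | +2 h | Day 1 pre-dose |
| As above, +2 h missing | +1 h | Day 1 pre-dose |
| As above, Day 1 pre-dose missing | +2 h | Screening |
| Only +1 h and +2 h before Day 3 | +2 h | Missing |
| Screening and one pre-dose Day 1 value | Day 1 pre-dose | Day 1 pre-dose |

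In the fourth row the two sentences of SAP 3.1.1 contradict each other outright: the first supplies +2 h, the second says missing. The last row shows that assessments made once before dosing are unaffected.

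**Step 2. How many post-dose readings are involved?** Per parameter and subject, the scheduled post-dose readings are +1 h and +2 h on Day 1, plus V3 to V9 (Days 3, 7, 11, 15, 29, 57 and 85): 2 + 7 = 9.

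**Step 3. Which count as post-baseline?** The term is undefined, so take each natural meaning, with +2 h as baseline.

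- *Later than the baseline record:* V3 to V9 only, 7 of 9. The other 2/9 = 22.2% are not post-baseline. In the shift table +1 h is in neither column and +2 h only in the baseline column.
- *Dated after the dosing date:* the same 7 of 9.
- *Within the on-study period of SAP 3.1.3:* +1 h and +2 h enter the maximum and minimum, but so does the Day 1 pre-dose reading, because that period is also set by date. The extremes are then taken over 1 + 2 + 7 = 10 readings, one of them untreated. Baseline is still +2 h.

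**Step 4. What would a shift table show?** Suppose, purely as an illustration, that a child's pulse is in range pre-dose and from Day 3 on.

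- *High only at +1 h:* a pre-dose baseline shows a normal-to-high shift. As worded, the first two meanings show normal to normal; the on-study meaning shows the shift.
- *High only at +2 h:* a pre-dose baseline shows normal to high. As worded, the first two meanings show high to normal, and the on-study meaning high to high. None shows a shift from normal.

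**Step 5. Which parameters?** Both pressures, pulse and respiratory rate in any case. Temperature is included under footnote c. If the separate line in Protocol 8.2.2 means that temperature is taken only before IP on Day 1, the point covers four of the five shift-table parameters. The 2-of-9 proportion for those four is unchanged.

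**The case against.** The best reply is that nobody meant a post-dose baseline. The second sentence of SAP 3.1.1 presupposes a pre-dose result, Protocol 8.3.11 describes a vital-signs assessment before IP, and SAP 3.4.3 promises changes to every later scheduled assessment. A competent programmer would probably take the pre-dose value. That stands as evidence of intent. It does not alter which value the first sentence selects when pre-dose and post-dose values both exist, and the SAP should not leave the choice to inference. Nor does the same-day rule in SAP 3.1.4 settle it: that rule picks a value for a visit, within windows that do not include Day 1, and does not redefine baseline.

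It is also fair to say that the loss of the two readings is not certain. It depends on the meaning of post-baseline, and the on-study meaning would bring them back, imperfectly.

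The consequence is modest too. This is a single-arm study of about 14 treated children with no hypothesis tests. All vital signs are listed with out-of-range flags, and investigator-judged abnormalities are summarised. Those outputs do not depend on baseline. A reader might infer that the sponsor chose a treated baseline, or that acute reactions would go unseen. The documents support neither: the surrounding text points to a pre-dose intent, and an abnormal 1-hour or 2-hour value would still appear in the listings and, where reported, among the AEs.

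**Conclusion.** The point holds as an internal inconsistency in SAP 3.1.1 that should be fixed. Followed literally, the first sentence makes a treated reading the vital-signs baseline. This holds under every meaning of post-baseline considered.

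The further statement that 2 of 9 scheduled post-dose readings per parameter (22.2%) drop out of post-baseline is conditional on that term meaning later than the baseline record or after the dosing date. These are counts of scheduled readings, assuming all are taken. They do not measure bias. The documents give no acute change in vital signs after dosing, so the actual distortion is unknown and may be zero.

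The reach is limited to the descriptive change and shift tables for vital signs. The primary PK endpoints are unaffected. Redacted sections may define other endpoint-specific baselines, but the vital-signs sections are readable and contain none.

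**What to change.** Change the SAP only.

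- **Section 3.1.1:** define baseline as the last valid, non-missing value recorded before the date and time of IP administration or, where an assessment has no recorded time, the Day 1 assessment scheduled as pre-dose. Put the same condition in the missing-baseline sentence so that the two agree.
- **Section 4.2.6.3:** state that the Day 1 1-hour and 2-hour vital signs are post-baseline time points, summarised as change from the pre-dose value and included in the maximum and minimum shift tables.
- **Section 6:** record this as a clarification of Protocol 9.4.1. That section is worded as a general rule and passes the detail to the SAP, so no protocol amendment is needed.

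The cost is a few sentences and two rows in the vital-signs table. No new assessments are required: Protocol 6.4 already has the date and time of IP administration recorded in the eCRF, SAP 3.1.4 already provides for assessment times, and the scheduled pre-dose fallback covers values without one.
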